### III. Clinician Measures: Implementation Outcomes

MBC Fidelity	1. If clients complete the PHQ-9, it will be captured in the EHR (0=No, 1=Yes). 2. The EHR will reveal whether clinicians reviewed scores (0=No, 1=Yes). 3. Clinicians will self-report if they discussed scores in session (0=No, 1=Yes). Clients will respond via text to indicate whether clinician initiated score discussion in session. Reasons for MBC fidelity deviation will be captured via clinician report on progress notes.	BL, AT2, AT3
--------------	---	--------------

*Note* BL(AT1) = Baseline(Assessment Time 1), AT2 = Assessment Time 2, AT3 = Assessment Time 3.

**Retention.** The total time required for clinician study participation is 15 months; however, the first two assessments are obtained within the first 5 months. The average length of employment for a clinician at Centerstone is 6 years with an average of 11.72% attrition last year. We anticipate stable clinician participation for the granting period. Fortunately, literature suggests that participatory approaches to organizational change in practice patterns result in lower clinician attrition (Minkler & Salvatore, 2012). Even so, we will recruit 1.25 times more clinicians ( $N=187$ ) to accommodate attrition and achieve the target ( $N=150$ ). Because of the dynamic waitlist design, we will revisit enrollment in Phase 2, 3 months prior to each site's planned implementation. Finally, the design can handle attrition given the within- and between-subjects analyses and multiple assessment points (3 ATs), as can the analyses (multilevel modeling with multiple imputation, described below).

### C12b. Depressed Adult Clients

**Recruitment.** Adult clients ( $N=625$ ; target  $N=500$ ) seeking treatment for depression at Centerstone will be eligible for enrollment in the research study. As this is a pragmatic trial (Thorpe et al., 2009) client participation criteria include: (a) age 18 and above; (b) depression is one of the primary treatment foci based on diagnosis made by clinicians using usual care interview methods to reflect major depressive disorder, dysthymic disorder, depressive disorder NOS, adjustment disorder with depressed mood; (c) significant depressive symptom severity (PHQ-9 total score  $> 9$ ); (d) receipt of individual psychotherapy; (e) fluency in English; and, (f) new client beginning treatment (g) with an enrolled study clinician during the proposed funding period. Exclusion criterion is minimal: an inability to sign the consent due to lack of competence or inability to read. Intake clinicians will be trained to identify eligible clients and assess if they would be interested in hearing more information about a research study. If the client agrees, the clinician will share the client's contact information with the project coordinator. Because Centerstone has a strong research commitment, clinicians and clients are accustomed to a research environment where the option to participate in studies is more routine than in many community mental health centers. Both Centerstone clinicians and clients have participated in a number of research studies and recruitment is expected to be very straightforward. However, to supplement this approach, Co-I ([name], Director of Centerstone Research Institute) will run weekly queries of the Centerstone database (in accordance with Health and Human Services guidance) to identify eligible clients (see Human Subjects for previously used HIPAA compliant procedures) who will be contacted by our project coordinator to assess interest in study participation. Once a client has been enrolled, the study team will flag the client in the electronic health record to initiate study procedures for the clinician. Given the number of clients seeking treatment for depression at Centerstone ( $> 30,000/yr$ ), we anticipate that our client recruitment goal will be feasible.

**Data Collection.** The goal of client data collection is to determine if routine measurement (in the standardized condition) improves depressive symptom severity and whether adaptations to the MBC assessment schedule (tailored condition) have differential effects on depression outcomes. Clients will complete the PHQ-9 on a tablet kiosk in the waiting room according to site-generated guidelines; this information will be automatically fed into the electronic health record for clinicians to review in session. Given the potential for variable PHQ-9 completion in the tailored condition (based on the site-generated guideline), we will also have clients enrolled in both conditions complete the PHQ-9 at baseline (immediately post consent) and at week 12 of treatment (via automated phone survey). The 12-week window

reflects a commonly used time period in randomized clinical trials during which depressive symptoms are expected to remit. We will also supplement data collection with client 5-axis diagnoses and employment status captured in intake and progress review reports.

**Retention.** At recruitment, clients will complete a consent form and provide options for multiple contact methods (e.g. multiple phone numbers, address). Centerstone has consistently achieved greater than 75% client retention in federally-funded randomized trials (CATIE, Keefe et al., 2007; STAR\*D, Insel, 2006). We will replicate previous efforts to maximize retention in the proposed study. In order to have sufficient power to detect statistical significance and account for client attrition, we intend to recruit 1.25 more client participants ( $N=625$ ) to assure that we achieve our enrollment goal ( $N=500$ ).

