## **C. Number of Subjects.**

### **Clinicians**

Clinicians will be recruited from 12 Centerstone sites across two states (Indiana and Tennessee). Approximately 187 clinicians (average of 16 per site) will be recruited during the latter half of Phase 1 of the study (months 5 to 8) to achieve our target enrollment of 150 (accounting for clinician turnover) and allow for initial site randomization (to early or late and standardized or tailored implementation) to occur just prior to Phase 2 (months 8-38).

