#### **Consenting Clients**

There is one pathway to identify clients for participation in the study. For full details on the recruitment process, please see the HIPAA Recruitment Checklist. There will be one Centerstone Research Institute research assistant (CRI RA) responsible for sites located in Tennessee and one CRI RA responsible for sites located in Indiana. Centerstone Research Institute has established a system for identifying clients eligible for the various ongoing research projects. Specifically, each CRI RA will run queries of the Electronic Health Record system database daily to identify potentially eligible clients seeking individual psychotherapy for depression with enrolled study clinicians based on the above listed inclusion/exclusion criteria (all eligibility information is collected during the intake and stored in the database). The average time from intake to the first psychotherapy session at Centerstone is 13 days, which will provide ample time for eligible clients to be enrolled in the study prior to the first therapy session. However, to ensure that the potential participant is contacted in a timely manner before their first psychotherapy session, the queries will be run daily. Upon identification of potential eligibility, the CRI RAs will contact the client via telephone within 24 hours to perform an eligibility 10-20 minute phone screen. The initial phone screen (RCR.3) is to confirm eligibility for participation, which is based on having a PHQ-9 score greater than 9 and a willingness to participate in the study. The CRI RA will verbally administer the PHQ-9 (in its entirety) to confirm project eligibility. If the client is determined to be eligible, the CRI RA will go over the informed consent statement (study procedure, risks/benefits, confidentiality, etc.) and ask the client if s/he is willing to give verbal consent to participation in the study at that time or if s/he would like to first receive and review the informed consent statement and the authorization for the release of protected health information. The CRI will stress that participation is voluntary and that the client may withdraw consent at any time. Following the phone call, consented participants and those interested in consenting upon review of the informed consent statement will be mailed a Welcome Packet, which will contain the informed consent for the client's records.

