Three days after the Welcome Packet is sent out, CRI RAs will then follow up with clients by telephone so that the client may have the opportunity to ask questions about the study. At this time, the CRI RAs may also offer to visit clients in person at their local Centerstone site or in their home (only if the RA is comfortable with this option) to discuss remaining questions about the research project further. Finally, although clinicians are not formally a part of the recruitment process, we have created an information sheet for clinicians in case his or her client has questions about the study the

clinician will be able to provide some background (RCR.8) and a client study brochure (Appendix F.2) that s/he can offer the client.

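### The plan describes two incompatible ways of identifying clients, and one lets site intake clinicians influence who is offered the study, mainly after sites are randomised

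*Combined protocol and SAP*

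**What the plan says.** The research plan and the human-subjects sections describe client recruitment differently.

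- **C12b, Recruitment.** "Intake clinicians will be trained to identify eligible clients and assess if they would be interested in hearing more information about a research study". The next step is "If the client agrees, the clinician will share the client's contact information with the project coordinator". To supplement this, the co-investigator who directs the research institute "will run weekly queries of the Centerstone database", and the project coordinator contacts the clients found that way.
- **Section XII, Consenting Clients.** "There is one pathway to identify clients for participation in the study". Here "each CRI RA will run queries of the Electronic Health Record system database daily to identify potentially eligible clients", and the section repeats that "the queries will be run daily" so that clients are reached before their first psychotherapy session. The research assistant telephones within 24 hours, administers the PHQ-9, confirms eligibility and seeks consent. On the clinicians' part, the section says "although clinicians are not formally a part of the recruitment process". They hold an information sheet and a brochure in case a client asks.

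On timing, Section V.C (Clinicians) has clinicians recruited in months 5 to 8 to "allow for initial site randomization (to early or late and standardized or tailored implementation) to occur just prior to Phase 2 (months 8-38"). Section V.C (Clients) puts client recruitment in Phase 2, stopping at month 35. The Overview under C. Approach has clients enrolled from the start of active implementation. Section VII differs in part: its Phase 1 summary lists client enrolment as beginning then, and it places the client telephone screen and consent under Phase 1.

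**The concern.** Sites, not clients, are randomised. Allocation by site protects the client comparison only if clients are then identified in the same way in both arms. If staff who may know their site's condition help decide which depressed clients hear about the study, the two client samples can differ for reasons unrelated to the effect of implementation. This is selection after randomisation, and with 12 sites there is little averaging to dilute it.

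H1b, the client half of the co-primary aim, and H3 both rest on this comparison. An intention-to-treat analysis keeps every enrolled client in the assigned arm, but it cannot restore clients who were never approached.

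**Working it through.** No figure in the plan is at issue, so the main check sets the texts side by side.

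**1. Can both descriptions be followed?**

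| Item | C12b, Recruitment | Section XII, Consenting Clients |
|---|---|---|
| Who identifies clients | Intake clinicians, with a query as supplement | Research assistants, by query only |
| Number of routes | Two | One |
| Query frequency | Weekly | Daily |
| First mention of the study | Intake clinician, or project coordinator for clients found by query | Research assistant, by telephone |
| Clinicians' formal role | Identify, gauge interest, pass on details | None |

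The number of routes, the query frequency and the clinicians' role each conflict. Both descriptions stand in current text.

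**2. Does identification come after randomisation?** Mainly yes. Section V.C puts site randomisation just before Phase 2 and client recruitment within it, and the Overview agrees. The Phase 1 statements in Section VII leave room for some earlier enrolment and also need reconciling.

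**3. Could site staff know the condition?** Table 3 gives each condition its own guideline, training and consultation focus. Section VII (Clinicians, Phase 2) describes training specific to the condition. Under C10, the implementation team at a tailored site sets the PHQ-9 schedule, and that team includes the site administrator and site clinicians. No masking of site staff is described. Awareness among intake clinicians is therefore plausible, but it is an inference.

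**4. Would the analysis remove a difference at entry?** C13a sets out the depression model under Aim 3. Intake and week-12 PHQ-9 are modelled with patient status as covariate and random intercepts for patient and clinic, and implementation group is then added. No group-by-time term is stated for implementation group, so a difference in severity at entry could pass into the group effect. The tests planned under Data screening can show imbalance only in measured variables.

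**5. Can the size be derived?** No. To show how open it is, let f be the share of enrolled clients who enter by clinician referral and whom the query would not have reached. Let δ be the between-arm difference among those clients, in SD units and in either direction. Then bias = f × δ. Both inputs are assumptions; the documents give neither. For scale, C13a states a smallest detectable client effect of d = .30 (two-sided alpha .05, power 80%). By normal approximation the implied standard error is 0.30 / (1.960 + 0.842) = 0.107. The false-positive rate is P(|Z + bias/SE| > 1.96).

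| f (assumed) | δ (assumed) | Bias, SD | Share of d = .30 | False-positive rate |
|---|---|---|---|---|
| 0, or any f with δ = 0 | any, or 0 | 0 | 0% | 5% |
| 0.25 | 0.1 | 0.025 | 8% | 5.6% |
| 0.50 | 0.2 | 0.10 | 33% | 15% |
| 1.00 | 0.3 | 0.30 | 100% | 80% |

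The range runs from no effect to the whole detectable effect, so it gives no estimate.

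**The case against.** The strongest reply is that this is a mismatch between a grant narrative and an operating procedure. Section XII is the more detailed text and already describes the sounder route. It also refers to a HIPAA recruitment checklist for full details, which is not among the documents. If the sites work to Section XII, clinicians refer nobody and the bias does not arise by this route. This stands in part: the risk depends on C12b being followed. But nothing in the documents says which text governs, so the contradiction remains.

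A reader might infer that under C12b site staff choose the client sample. The documents do not support that. C12b's own query can reach a client whom no clinician named, and the project coordinator then makes contact. Site staff can influence who is offered the study; they do not decide it alone.

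A reader might also infer that intake clinicians are known to be unmasked and inclined to refer differently. The documents do not say what intake clinicians know. Training is offered to enrolled clinicians, intake precedes the first psychotherapy session by 13 days on average (Section XII), and intake staff need not be the trained therapists. Knowing the local PHQ-9 schedule is also not in itself a motive for selective referral.

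Finally, baseline PHQ-9 is collected for every enrolled client and group comparisons are planned. These could reveal a measured imbalance, but they cannot show who was never approached.

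**Conclusion.** The contradiction is certain and must be resolved. Its consequence is conditional. If C12b is followed, site staff can influence who is offered the study, mainly after their site's allocation, and identification could differ between arms for H1b and H3. That step rests on the timing in Section V.C and the Overview, on guidelines and training that differ by condition, and on the absence of any described masking.

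A reader might take the illustration as showing a bias of some definite fraction of the detectable effect. It does not. Every input except d = .30 with its alpha and power is assumed, zero lies within the range, and the bias from identification is zero if the query reaches every eligible client. The change is worth making because it closes an avoidable route to bias at little cost, not because a bias has been shown.

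**What to change.** Remove the intake-clinician referral route and the weekly query from C12b. Make the daily research-assistant query in Section XII the only route at all sites, and require that every client it identifies is contacted. Align the Phase 1 and Phase 2 statements on when client enrolment starts.

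Report by site and condition the numbers identified, contacted, screened, eligible and consented, with baseline PHQ-9 by condition.

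Parts of C13a are in the past tense and report that 22.8% of patients did not complete the 12-week interview, so recruitment may be complete. If it is, state which route was used, give the same counts as far as records allow, and, if clinician referral occurred, compare results by route.

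The cost is small. The daily query and its staff are already in the plan. What is added is a simple log and a rule that all identified clients are contacted. Some clients whom a clinician would have named and the query misses will not be approached; the documents do not show how many. One limit remains: under Section V.B the qualifying diagnosis is made by site clinicians in usual care, and the query reads data collected at intake, so some site influence on who is identified stays. The counts by site and condition would help show whether it differs between arms.

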By design, MBC has great potential for implementation success, yet barriers such as attitudes (perceptions that standardized measures have limited utility) and feasibility (perceptions that measures take too much time) exist (Garland et al., 2003), and the gap between documented MBC effectiveness and use in practice remains. Research to date has largely focused on evaluating standardized approaches to implementation, despite a recent Cochrane meta-analysis highlighting the potential impact of tailoring implementations (Baker et al., 2009). There is a crucial need for process-focused implementation research. Hence our proposed comparison of implementation conditions (i.e., standardized versus tailored) is *both clinically and scientifically significant* because it will (a) reveal whether standardized or tailored approaches to implementation optimize MBC fidelity, (b) enhance our understanding of both theory and processes for standardized versus tailored implementation; and, (c) illuminate predictors, moderators, and mediators of successful implementation. Our proposed implementation-effectiveness hybrid design will yield important insights regarding MBC clinician level implementation outcomes. It will simultaneously shed light on the effect of MBC on adult mental healthcare for depression in

community settings when adapted by stakeholders to fit their context. Our research will answer the how of implementation by evaluating the effect of contextual factors on the process, an effort that directly aligns with NIMH's Strategic Plan 4.1 to "Improve understanding of the factors that affect...the means by which newly discovered effective mental health interventions are disseminated and implemented."

**B2. INNOVATION.** *This proposal is innovative in at least three ways.*

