## **C. APPROACH**

**Overview.** Given the underwhelming use of MBC in community mental health settings coupled with the demand for performance outcome assessment (Affordable Care Act), this randomized implementation trial aims to compare the effectiveness of a standardized versus tailored approach to implementation of MBC with co-primary outcomes at the clinician (MBC fidelity) and client (depression severity) levels. We will randomize 12 sites of a large community mental health center (Centerstone) to early or later stage standardized or tailored implementation enrolling 150 clinicians and 500 depressed clients in a pragmatic trial (Thorpe et al., 2009). The main clinician level outcome is MBC fidelity, defined as (a) client completion of the PHQ-9, (b) clinician review of scores in the electronic health record, and (c) discussion of scores in session. Phase 1 (months 0-8) will interface the most widely used and validated depressive symptom severity measure (Patient Health Questionnaire-9 item; PHQ-9; [name], 2001) with the electronic health record; this measure is the main client level outcome. Phase 2 (months 8-38) constitutes the active implementation (5 months) and sustainment (10 months) phase. In both conditions, clients will have the option to complete the PHQ-9 on tablets in the waiting room prior to session, which will feed scores to clinicians via the electronic health record. Sites randomized to the standardized condition will begin with a baseline mixed methods needs assessment (for the purposes of putative mediator data collection) and receive the guideline that MBC is to be used in each session with a depressed client. The standardized condition will include manualized training and triweekly group consultation with experts to promote MBC fidelity and optimize its clinical utility. An implementation team (including a site administrator, opinion leader, MBC champion, and research personnel) will convene prior to each triweekly group consultation to review progress and troubleshoot problems. Sites randomized to the tailored condition will also begin with a needs assessment to identify contextual factors that may serve as barriers to the implementation (guided by the *Framework for Dissemination*; [name] et al., 2008; see C7). Training and triweekly group consultation will be tailored to address these barriers (e.g., clinician attitudes toward MBC). The implementation team (same composition as in standardized) will define a site-specific guideline for MBC use (e.g., monthly) and convene prior to each triweekly group consultation to troubleshoot MBC fidelity barriers. At the start of the active implementation across both conditions, depressed clients of participating clinicians will be enrolled to compare the effect of standardized versus tailored MBC implementation on client outcomes. Phase 3 (months 38-48) will characterize MBC fidelity using electronic health record data capture. The evaluation approach is guided by the *Framework for Dissemination* ([name] et al., 2008) and includes a baseline needs assessment, implementation/process evaluation (5 months into implementation), and outcome/impact evaluation (15 months into implementation). This design will allow for a direct test of the assumption that voltage drop in treatment outcomes occurs in the context of adapting the intervention to fit the context (Chambers et al., 2014), while simultaneously exploring the effect of standardized and tailored approaches to MBC implementation.

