## **C10. Multifaceted Standardized and Tailored Implementation Conditions**

***Overview of the Blended Implementation Protocol.*** Both conditions (standardized and tailored) will employ the same blended protocol of implementation strategies to remove time and resource confounds (see Table 3). The guiding model (*Framework for Dissemination*; Figure 1; [name] et al., 2008), the best available literature on related efforts to promote MBC implementation (e.g., Evans & Hser, 2004; Harding et al., 2011; Lambert et al., 2005; Morris & Trivedi, 2011; Persons, Hong, & Koerner, 2012; Teruya, [name], Hser, & Evans, 2006), personal communication regarding program evaluation of a loosely tailored MBC implementation effort at Group Health clinics ([name], February 11, 2014), the MBC intervention framework, the partnership goals, and the pilot study defined the blended protocol of implementation strategies (Powell, McMillen, Proctor, et al., 2012). It was determined that embedding the PHQ-9 into the electronic health record was not sufficient but that using tablet computers would be essential to promote feasibility of implementation. The proposed local needs assessment is necessary to assess site-specific contextual factors and to identify opinion leaders and champions. In our pilot, we did not involve clinicians on the implementation team, but literature suggests this may be critical to achieving sustainment (Teruya, [name], Hser, & Evans, 2006) and it is consistent with our partnership goals. As such, each site will form an implementation team consisting of the PI, Co-I ([name]), the site administrator, a clinician identified as an opinion leader (via self-report; Childers, 1986), and a self-nominated MBC champion who will meet for at least 30 minutes prior to each triweekly consultation session. Training and consultation with experts are essential strategies for promoting clinician behavior change and fidelity to the intervention, particularly in the case of evidence-based psychosocial interventions (Herschell et al., 2010). A guideline will be set to specify the frequency of expected PHQ-9 administration with depressed clients. The order of strategies will proceed as follows within each site's 5-month active implementation period: (a) embed PHQ-9 in electronic health record; (b) conduct needs assessment; (c) form implementation team; (d) set guideline; (e) offer initial training; (d) conduct tri-weekly group consultation meetings (see C11. Overview of Study Design). In the 10 months post active imple-

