implemented using the R lmerTest package with a random intercept for clinic. The b path was assessed using generalized linear mixed models with a logit link function for a binary distribution using the lme4 package. **Aim 3 Hypotheses:** Adapted MBC protocols (i.e., tailored condition) will outperform routine weekly administration of PHQ-9s (i.e., standardized condition) with respect to clinically significant change in depression severity from intake to week 12. Depression severity was analyzed using linear mixed models with Satterthwaite degrees of freedom implemented using the R lmerTest package. Multiple imputation was used to estimate missing values across 20 datasets in which 22.8% of patients did not complete the 12-week interview. We first assessed whether there was a change in PHQ-9 between intake and week 12 in a mixed model containing patient status as a covariate and random intercepts for patient and clinic. Next, implementation group was added to the model. In addition, number of sessions, number of sessions that the PHQ-9 was recorded, and number of sessions that the PHQ-9 was discussed were added to the model. We also examined the interactions between new patient status and the focal variables. **Power calculations.** A power analysis for the multilevel models for Aim 1 was assessed with Monte Carlo studies in which power is the proportion of significant effects (2-tailed  $\alpha$ ,  $p < .05$ ) for parameters of interest observed over repeated analyses of simulated data (Muthén & Muthén, 2002; Thoemmes, Reiser, & MacKinnon, 2010) using MPlus (version 7). For each model, 10,000 data sets were simulated and analyzed. Data in the Monte Carlo studies were simulated with the goal of identifying the smallest detectable effect size with power  $> 80$ . Dropout was simulated to reflect an increase of 5% missing data per wave. Repeated measurements were nested within participants (ICC = .50) and participants were nested in sites (ICC = .05). Average effect sizes for Aim 1 analyses were computed using an approximation of Cohen's  $d$  for growth models (Feingold, 2009). Using this metric, we are sufficiently powered to detect effect sizes as small as  $d = .46$  for the clinician models ( $N = 150$ ) and effect sizes as small as  $d = .30$  for the client models ( $N = 500$ ). For Aim 2, we conducted power analyses for the hypothesized mediation effects with the same assumptions described above but with the use of effective samples size estimates (an ICC corrected sample size) based on a design effect adjustment (Bickel, 2007) in order to use standard effect size metrics. The  $\kappa^2$  effect size for mediation (.01, .09, and .25 represent small, medium, and large  $\kappa^2$  respectively) was computed (Preacher & Kelly, 2011). We are sufficiently powered to detect effect sizes as small as  $\kappa^2 = .16$  for the clinician models and effect sizes as small as  $\kappa^2 = .10$  for the client models. For Aim 3 analyses, we are sufficiently powered to detect effect sizes as small as  $r = .27$  for clinicians and as small as  $r = .21$  for clients. The planned sample sizes are consistently sufficient for detecting medium effect sizes for clinician outcomes and small effect sizes for client outcomes, with the power to treat site as a random effect based 6 sites per condition (Atkins & Baldwin, 2013).

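### The first half of the client-level goal, whether routine measurement improves depression, has no comparator without MBC, so this design cannot answer it

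*Combined protocol and SAP*

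**What the plan says.** Section C12b (Data Collection) puts two questions in one sentence. The first is "The goal of client data collection is to determine if routine measurement (in the standardized condition) improves depressive symptom severity". The second is "whether adaptations to the MBC assessment schedule (tailored condition) have differential effects on depression outcomes".

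Both arms receive MBC. Section C10 says "Both conditions (standardized and tailored) will employ the same blended protocol of implementation strategies", and the Overview in section C says "In both conditions, clients will have the option to complete the PHQ-9 on tablets in the waiting room prior to session". Section C15 assigns half the sites to each approach. On entry of clients, the Overview says "At the start of the active implementation across both conditions, depressed clients of participating clinicians will be enrolled".

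The Aim 3 text in C13a gives the client analysis in steps. It begins "We first assessed whether there was a change in PHQ-9 between intake and week 12", using a mixed model with patient status as a covariate and random intercepts for patient and clinic. Implementation group is added next. Three counts are then added: sessions, sessions with the PHQ-9 recorded, and sessions with the PHQ-9 discussed.

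C12b justifies the 12-week window as a "commonly used time period in randomized clinical trials during which depressive symptoms are expected to remit". Entry requires a PHQ-9 above 9 (C12b, Section V and Section XII; the phone-screen text in Section VII says 9 or higher).

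**The concern.** Whether routine measurement improves depression is a question about MBC against its absence. A reader looking for the plan's answer finds the first modelling step in C13a, a before-and-after change. A fall in PHQ-9 is likely there whether or not MBC does anything: clients enter with raised scores, all are in psychotherapy, medication is not excluded (Section VII collects it), and remission is expected in the window. Nothing in C13a marks the step as descriptive.

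At stake is what the trial may conclude. Section C16, repeated in Section VIII, says positive findings would offer a workable and effective way to reduce the burden of depression. A significant pooled fall could be mistaken for such a finding.

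**Working it through.** **1. Match each question to a comparison.**
- Adapted versus standard schedule: randomised, 6 sites against 6. Answerable in principle.
- Routine measurement versus none: no site is assigned to go without MBC, and no client model in C13a has a term for waiting versus implementing. Not answerable.

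**2. Could the waitlist supply the missing group?** Cohorts start 5 months apart from month 8 (C11), so the fourth starts at about 8 + 3 × 5 = month 23. The Overview enrols clients at the start of active implementation. Section VII says client enrolment begins in Phase 1 (months 0-8), and Section V recruits at the 12 sites from month 8 to 35. Some clients might therefore be seen before their site implements MBC, but no planned analysis uses them.

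**3. What the remaining analyses estimate.** The change step precedes the group term, so it pools the arms and does not isolate the standardized condition that the goal names. The recorded and discussed counts are non-randomised dose associations, open to confounding by attendance and severity. The client power figure in C13a (d = .30, N = 500) is for Aim 1, which compares the arms; no power statement covers MBC against no MBC.

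**4. How large a fall could selection alone produce?** Assume normal scores with mean μ and SD σ in the source population, correlation r between screening and week 12, the screening score used as baseline, a cut at 9.5, and no treatment effect or natural recovery. Then

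a = (9.5 − μ)/σ; λ = φ(a)/(1 − Φ(a)); expected fall = (1 − r) σ λ.

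The plan gives no μ, σ or 12-week r for PHQ-9. Its only related figure is a repeated-measures ICC of .50 in the power section. Assumed ranges: μ 8 to 14, σ 5 to 6, r .5 to .85.

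| μ | σ | r | a | λ | Expected fall |
|---|---|---|---|---|---|
| 8 | 6 | .50 | 0.25 | 0.964 | 0.50 × 6 × 0.964 = 2.89 |
| 12 | 6 | .50 | −0.417 | 0.553 | 0.50 × 6 × 0.553 = 1.66 |
| 14 | 5 | .85 | −0.90 | 0.326 | 0.15 × 5 × 0.326 = 0.24 |

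The first and last rows are the extremes. At r = .50 throughout, the range is 0.82 to 2.89.

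**5. Would a test of no change reject?** The variance of change after selection is (1 − r)²σ²(1 + aλ − λ²) + σ²(1 − r²). Take 500 × 0.772 = 386 clients, applying the 22.8% without a week-12 interview to the target of 500.
- First row: variance 29.81, SD 5.46, SE 5.46/√386 = 0.278. The fall is 2.89/0.278 = 10.4 SE, so rejection at two-sided 5% is practically certain.
- Last row: variance 7.28, SD 2.70, SE 0.137. The fall is about 1.8 SE, and the rejection probability is 0.43.

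With n = 500 the range is 0.53 to 1.00. These figures treat clients' changes as independent; site-to-site variation in change would widen the SE.

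**6. Dependence on the baseline.** Section VII uses the phone-screen PHQ-9 as baseline. C12b describes a baseline PHQ-9 immediately after consent. If that is a separate measurement, and its correlation with screening equals that of week 12, both have expectation μ + rσλ given selection, and this artefact vanishes. Natural recovery and psychotherapy would remain.

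**The case against.** The strongest reply is that nothing formal depends on the clause. H1b and H3 compare tailored with standardized implementation, the Overview gives that comparison as the reason for enrolling clients, and section B1 treats MBC's effectiveness as already established. C13a attaches no conclusion about MBC to the change step, which resembles the time-only models fitted before group in Aim 1. This stands and limits the point to one stated goal. It does not remove it: if effectiveness is taken as given, C12b should not set out to determine it.

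Three stronger readings are tempting, and the documents do not support them.
- A reader might infer that the change step is the only analysis touching the question. The session counts, and Aim 3's exploration of fidelity against outcome, also touch it, though they supply no comparator.
- A reader might take B1's "It will simultaneously shed light on the effect of MBC on adult mental healthcare for depression" as a claim that the trial tests MBC itself. The sentence goes on to limit this to MBC adapted by stakeholders in community settings, which the trial does compare with the standardized form. C16 is likewise conditional on positive findings. Neither text needs deleting.
- A reader might infer that regression to the mean makes a significant fall certain. Step 5 shows it need not, and step 6 shows it depends on which baseline is used.

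**Conclusion.** The concern holds for the first clause of the C12b goal only. That clause cannot be answered because no group goes without MBC and no client model uses the waiting period. This conclusion rests on the design and needs no numerical assumption.

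The size of the artefact is illustrative: about 0.2 to 2.9 points, with every input assumed. Even the upper end is below the 5-point change that C4 calls clinically significant, but expected remission and psychotherapy would add to it. The randomised contrast, and H1b and H3 that rest on it, are not called into question.

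**What to change.** - **C12b, Data Collection:** restrict the goal to whether the week-12 PHQ-9 outcome differs between tailored and standardized implementation.
- **C13a, Aim 3:** label the intake-to-week-12 step descriptive and the session-count terms associational. State that neither is evidence of an MBC effect, and reserve inference for the between-arm contrast.
- **C12b and Section VII:** reconcile whether the baseline is the screening score or a separate measurement after consent.
- **C16 and Section VIII:** keep the text, but read its effectiveness statement as resting on the between-arm result only.

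No procedure or sample size changes for the goal and labelling edits. The price is a narrower claim: the trial can report comparative effectiveness of two implementation approaches, not effectiveness of MBC.
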